Amendment 1	13-Apr-2020	2019N416505_01
Original Protocol	7-Jan-2020	2019N416505_00

Amendment 2: 30-JUN-2021

Overall Rationale for the Amendment: A Dear Investigator Letter (DIL) dated 13-April-2021 was issued requiring the stopping of further screening and the discontinuation of the administration of GSK3359609 (feladilimab) or placebo for all participants on INDUCE-4, effective immediately. Further to the DIL, since all participants have the option to remain on pembrolizumab alone plus 5FU-platinum as study therapy, GSK issued a Protocol Clarification Letter (PCL) dated 28-April-2021 to reduce any unnecessary burden of on treatment and follow up assessments (the PCL did not alter any screening assessments). This protocol amendment is a follow up to the PCL, with a primary intent to only update the SoA; other impacted, relevant sections were also updated accordingly. Additionally, updates were made to management guidelines to align with pembrolizumab IB update.

Section # and Name	Description of Change	Brief Rationale
1.3 Schedule of Activities (SoA)	Assessments related to GSK3359609 (feladilimab) were removed. These include feladilimab/placebo infusions; feladilimab PK collections, immunogenicity, IRR lab panel, plasma collections, PBMC collections, optional biopsy, Patient Reported Outcomes (PROs), Healthcare Resource Utilization (HCRU), prior protocol required disease assessments, follow-up subsequent anticancer therapy and disease assessments, and pembrolizumab second course. Minor clarifications to pembrolizumab dosing and window extension to PE, PS, and vital signs were also added.	Since there will be no further screening into the study and no further dosing of GSK3359609 or placebo, there is no need to collect samples, PROs or efficacy assessments to determine the effect of GSK3359609

Section # and Name	Description of Change	Brief Rationale
6 Study Intervention	Added reference to Schedule of Assessments.	To align with updated SoA.
6.1.1 Duration of Second Course	Removed section.	Second Course will not be administered as subsequent anticancer therapy will not be followed and PFS2 will not be analysed as the study is terminated with no further screening.
6.6.1 General Guidelines for Immune-Related Adverse Events	Added neurological toxicities and exfoliative dermatological conditions as immune-related AEs and updated myocarditis information.	To align with pembrolizumab IB update (Edition 20 March 2021).

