9.4.3. Patient Reported Outcomes

EORTC IL50 and IL51(subset of domains from the EORTC QLQ C30 and H&N35 respectively) are not pure efficacy or safety endpoints because they are affected by both disease symptoms and treatment tolerability in addition to HRQoL domains.

The time to deterioration (TTD) in Pain measured by the EORTC QLQ-H&N35 pain domain (included in the EORTC IL51) and the TTD in Physical Function (PF) measured by the PROMIS PF 8c will be analysed in the ITT population using the non-parametric Kaplan-Meier method.

The treatment effect in TTD will be assessed separately by the stratified log-rank test. A stratified Cox proportional hazard model with Efron's method of tie handling will be used to assess the magnitude of the treatment difference (i.e., hazard ratio) between the treatment arms. The hazard ratio and its 95% confidence interval from the stratified Cox model with Efron's method of tie handling and with a single treatment covariate will be reported.

For both Pain and PF, TTD will be defined as the time from the date of randomization to the date of first definitive meaningful deterioration in score compared to baseline. The deterioration has to be:

- Meaningful, i.e. greater than a clinically meaningful within-individual change in score, as defined below;
- Definitive, i.e. two sequential assessments of the score are showing a clinically meaningful deterioration compared to baseline and no subsequent scores return to baseline, or no further score is available for the patients for any reason (including disease progression or death)

Patients who don't show meaningful deterioration will be censored at the time of the last available PRO assessment.

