4.3. Secondary Endpoint(s) Analysis

4.3.1. Key/Confirmatory Secondary Endpoint(s)

4.3.1.1. Definition of Endpoint

Time to Deterioration (TTD) in Pain and Physical Function (PF)

Time to deterioration (TTD) is defined as the time from randomization to the first definitive meaningful deterioration from baseline in the EORTC IL51 pain domain score and the TTD in Physical Function (PF) score. Deterioration is defined as an increase in the EORTC IL51 pain domain and a decrease in physical function as measured by the PROMIS-PF-8c. Specifically, the deterioration has to be:

- Meaningful, i.e. greater than a clinically meaningful within-individual change in score, as defined below;
- Definitive, i.e. all subsequent assessment of the score are also showing a clinically meaningful deterioration compared with baseline, or no further score is available for the participants for any reason (including discontinuation, disease progression or death).

Participants who don't show meaningful deterioration will be censored at the time of the last available PRO assessment within the pain domain of EORTC IL51 for TTD in pain or within PROMIS-PF-8c for TTD in PF. For TTD in pain or TTD in PF, the determination of dates of deterioration events and dates for censoring are summarized in [Table 4](#).

Table 4 Censoring Rules for Analysis of TTD

Situation	Primary Analysis
No or incomplete baseline corresponding PRO assessments	Censored at the date of randomization
No post-baseline corresponding PRO assessments	Censored at the date of randomization
With post-baseline corresponding PRO assessments, new anticancer treatment is not initiated, and no deterioration	Censored at the date of last available corresponding PRO assessment
With post-baseline corresponding PRO assessments, and new anticancer treatment is initiated (prior to deterioration) ¹	Censored at the date of last available corresponding PRO assessment on or prior to starting new anticancer treatment
Deterioration after ≤ 1 missed corresponding PRO assessment ²	Deteriorated at the date of deterioration
Deterioration after ≥ 2 missed corresponding PRO assessments if at least one missed assessment is due to the participant being too ill ^{2,3}	Censored at the date of last available corresponding PRO assessment prior to the ≥ 2 missed corresponding PRO assessment

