4.3.1.2. Main analytical approach

PFS per RECIST v1.1 in PD-L1 CPS ≥ 1

PFS per RECIST v1.1 in PD-L1 CPS ≥ 1 participants will be analyzed and reported similarly to the primary analysis of PFS in PD-L1 CPS all participants as described in Section 4.2.2.

Time to Deterioration (TTD) in Pain and Physical Function (PF)

The time to deterioration (TTD) in Pain measured by the EORTC IL51 pain domain and the TTD in Physical Function (PF) measured by the PROMIS-PF-8c will be analyzed separately for the PD-L1 total and CPS ≥ 1 group using the non-parametric Kaplan-Meier method. Kaplan-Meier plots of TTD will be presented by study intervention. Kaplan-Meier estimates for the median TTD and the first and third quartiles will be presented, along with 95% CIs. CIs for quartiles will be estimated using the Brookmeyer-Crowley method (1982). The TTD for both treatment groups will be compared by the stratified log-rank test.

A stratified Cox proportional hazard model with Efron's method of tie handling will be used to assess the magnitude of the treatment difference (i.e., the hazard ratio). The hazard ratio and its 95% confidence interval from the stratified Cox model with a single treatment covariate will be reported separately for the PD-L1 total and CPS ≥ 1 group. Participants with no post-baseline assessments will be considered censored at day 1 and participants without definitive meaningful clinical deterioration for the PRO score will be treated as censored for that PRO score at the last visit.

Only if GSK3359609 in combination with pembrolizumab + 5FU/platinum-based chemotherapy demonstrates superiority to placebo in combination with pembrolizumab + 5FU/platinum-based chemotherapy in OS in both populations (total and PD-L1 CPS ≥ 1 participants), will key secondary PRO endpoints be tested. The alpha level from OS hypothesis will be propagated to key PRO hypotheses as described in Section 2.2.

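### After the sponsor ended PRO collection, the SAP's TTD rule counts a single deteriorated last score as a definitive event

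*SAP*

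**What the plan says.** **Definition of the event.** SAP 4.3.1.1 requires a deterioration to be meaningful and definitive. Definitive is met in either of two ways. The first is "all subsequent assessment of the score are also showing a clinically meaningful deterioration compared with baseline". The second is an alternative that needs no later score at all: "or no further score is available for the participants for any reason (including discontinuation, disease progression or death". Protocol 9.4.3 is worded differently. It asks for two sequential deteriorated scores with no return to baseline, and then adds "or no further score is available for the patients for any reason".

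**Censoring.** SAP 4.3.1.2 says that "participants without definitive meaningful clinical deterioration for the PRO score will be treated as censored for that PRO score at the last visit". SAP Table 4 gives the row-by-row rules.

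**End of PRO collection.** The Amendment 2 summary of changes gives the sequence. "A Dear Investigator Letter (DIL) dated 13-April-2021 was issued requiring the stopping of further screening"; GSK3359609 and placebo were stopped for everyone at the same time. Then "GSK issued a Protocol Clarification Letter (PCL) dated 28-April-2021 to reduce any unnecessary burden of on treatment and follow up assessments". The items that Amendment 2 took out of the schedule include "optional biopsy, Patient Reported Outcomes (PROs), Healthcare Resource Utilization (HCRU), prior protocol required disease assessments", because "there is no need to collect samples, PROs or efficacy assessments to determine the effect of GSK3359609". The current Schedule of Activities has no PRO row. Participants could stay on pembrolizumab plus chemotherapy.

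**Reporting.** SAP Section 1 keeps all secondary endpoints, including both TTD endpoints, in the main CSR. SAP 4.2.3, 4.2.4 and 4.4 drop sensitivity, supplementary and exploratory analyses.

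**The concern.** Accepting a missing later score as confirmation makes sense when the score is missing because the participant died, progressed or left. Here the PRO series of everyone still contributing ended by sponsor decision, so the last score falls where the calendar put it and says nothing about the participant's course.

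Transient threshold crossings are plausible at that point. Chemotherapy runs for six 21-day cycles, about 18 weeks, and PROs were 3-weekly to Week 21 (SAP 5.3), so recent enrolees would have been cut off during chemotherapy. The pain domain is mouth pain (Protocol 8.11.1), and mucositis occurred in 2 of 6 participants in the chemotherapy run-in cohort, at a different GSK3359609 dose (Protocol 2.2.1.1). A participant with only a Week 3 score has no way to show recovery.

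SAP version 3 adapted the TTD threshold procedure and the analysis set to early termination, but left this clause alone. At stake are the TTD event counts, Kaplan-Meier medians and hazard ratios in the main CSR. These are the only PRO comparisons left in it.

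**Working it through.** **1. Plan figure.** There is none to reproduce. The documents give no TTD event count, rate, power or hazard ratio, and no accrual.

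**2. One case through the rule.** Take a participant still on pembrolizumab, not deteriorated at Weeks 3 and 6, first deteriorated at Week 9, with no further PRO because collection ended.

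- SAP 4.3.1.1: no later score exists, so the second branch makes the deterioration definitive.
- Table 4: the rows for no baseline, no post-baseline PRO, no deterioration, and new anticancer therapy before deterioration do not apply. Nor does the row for two or more missed assessments with illness. The row for at most one missed assessment applies: event at Week 9.
- Table 2: the TTD intercurrent events are new anticancer therapy, treatment discontinuation, progression, death, and missed assessments with illness. The sponsor's end of collection is not listed.
- SAP 4.3.1.2: its censoring sentence covers only participants without a definitive deterioration, so it does not help.

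Had recovery been recorded at Week 12, the first branch would fail, the second would not apply, and Week 9 would not be an event.

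**3. The protocol's wording.** It has two readings:

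- (two sequential scores and no return) or (no further score): Week 9 is an event, as in the SAP.
- two sequential scores and (no return or no further score): Week 9 is not an event.

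The SAP drops the two-score wording. Neither SAP 1.1 nor the version history lists the change.

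**4. Size for one stable participant.** Let p be the chance of a transient crossing at a visit, independent across visits. The chance of a false event at cut-off is p under the SAP rule and at most p² if two sequential scores are needed: 5% against 0.25%, 10% against 1%, 20% against 4%.

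**5. Illustrative simulation (200,000 per arm).** From the SAP: PROs 3-weekly to Week 21, then 6-weekly. Assumed: uniform accrual over 38 weeks (20 July 2020 to 13 April 2021); PRO stop at week 40 (28 April 2021); exponential permanent deterioration; independent transient crossings; no other PRO dropout. The comparator needs two sequential deteriorated scores and censors otherwise at the last PRO. The ratio is events per unit of person-time; true hazard ratio 0.70.

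| p | Control median, weeks | Control events, SAP / two-score | False share of control events, SAP / two-score | Rate ratio, SAP / two-score |
|---|---|---|---|---|
| 0.05 | 26 | 40.1% / 31.0% | 7.6% / 0.4% | 0.731 / 0.699 |
| 0.05 | 52 | 25.2% / 17.6% | 15.3% / 1.0% | 0.750 / 0.699 |
| 0.10 | 26 | 43.1% / 31.7% | 14.2% / 1.7% | 0.755 / 0.706 |
| 0.10 | 52 | 28.9% / 18.3% | 26.3% / 3.7% | 0.799 / 0.721 |
| 0.20 | 26 | 49.2% / 34.0% | 24.6% / 6.3% | 0.791 / 0.724 |
| 0.20 | 52 | 36.6% / 20.9% | 41.5% / 13.3% | 0.836 / 0.736 |

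Under the SAP rule, 22% to 43% of control events rest on a single last score. With a true hazard ratio of 1.0 the ratio is 0.99 to 1.01 under both rules.

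**6. Other assumed inputs.** A second simulation assumed enrolment over 6 or 10 months, a control median of 6, 9 or 12 months, 8% per month leaving PRO follow-up, and a transient crossing at the last PRO in 10% to 30% of participants without a true event. It moves 0.70 to about 0.75 to 0.89. The administrative stop alone makes 4% to 19% of all participants false events, which is 13% to 62% of counted events. Across both simulations the range is 0.73 to 0.89.

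**The case against.** Several points on the other side stand.

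- **The clause predates termination.** It is in Protocol 9.4.3 and would operate at any data cut-off. Termination widens its reach to everyone then completing PROs.
- **The stop date is inferred.** The text naming PROs as removed is in Amendment 2. The April letter is described only as reducing burden. Protocol 10.1.1 requires ethics approval before amendment changes are implemented, so the stop may have varied by site. PROs are still mentioned in SoA footnote 1 and Section 8.11, but the SoA schedules none.
- **The size is assumed throughout.** The prevalence of transient crossings drives it, and dilution needs a true benefit to dilute. Some last scores would have been confirmed.
- **The consequence is limited.** PRO hypotheses are tested only if OS is superior in both populations (SAP 2.2, 4.3.1.2), and the study was terminated.
- **Handling may sit elsewhere.** The version history moves PRO details to a standalone SAP, and Section 1 moves data conventions to the OPS. Neither is available here. Even so, SAP 4.3.1.1 and Table 4 would contradict any different rule there.

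A reader might infer that the flaw is the same under the protocol's wording. The documents do not support that, because the second reading of Protocol 9.4.3 never counts a single last score. A reader might also infer a bias favouring one arm. The stop applied to both blinded arms, and the simulated ratio under the null stays at about 1.

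**Conclusion.** The point holds as a defect of the event definition: followed as written, the SAP counts an unconfirmed, possibly transient last score as definitive when the only reason for the missing next score is that the sponsor ended collection. No censoring row, intercurrent-event strategy or planned analysis would prevent or reveal it. The unrecorded departure from the protocol's two-score wording makes it worse.

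The direction is clear: extra false events, shorter TTD in both arms, and a hazard ratio closer to 1 if GSK3359609 truly delays deterioration. The figures show only that the effect need not be trivial. They cannot be read as an estimate for this trial, because accrual, TTD rates and the frequency of transient deterioration are not in the documents. Type I error is not inflated. For a descriptive secondary endpoint this is a cheap correction worth making.

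**What to change.** 1. Reconcile SAP 4.3.1.1 with Protocol 9.4.3 on whether two sequential deteriorated scores are required, and record the choice in SAP 1.1.
2. Accept a missing later score as confirmation only for participant-level reasons: death, disease progression, withdrawal, or permanent discontinuation of all study treatment. State that stopping GSK3359609/placebo under the letter of 13 April 2021 is not such a reason; otherwise the exception could cover everyone.
3. Add a Table 4 row and a Table 2 intercurrent-event strategy for participants still in PRO follow-up when collection ended. Use their last PRO only to confirm an earlier deterioration. Censor all of them without a confirmed deterioration at the preceding PRO (randomization if none), whatever the last score.
4. Report by arm how many events rest on a single last score under the current rule.

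The censoring in item 3 must not depend on the last score. Censoring only participants whose last score is deteriorated keeps the hazard ratio near 0.70 but biases TTD long: under the second set of assumed inputs it understates the control event rate by about 8% to 18%.

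The cost is SAP wording and one derivation flag, with no new data. Some true but unconfirmed events and a little follow-up time are lost.

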4.3.1.2. Main analytical approach

PFS per RECIST v1.1 in PD-L1 CPS ≥ 1

PFS per RECIST v1.1 in PD-L1 CPS ≥ 1 participants will be analyzed and reported similarly to the primary analysis of PFS in PD-L1 CPS all participants as described in Section 4.2.2.

Time to Deterioration (TTD) in Pain and Physical Function (PF)

The time to deterioration (TTD) in Pain measured by the EORTC IL51 pain domain and the TTD in Physical Function (PF) measured by the PROMIS-PF-8c will be analyzed separately for the PD-L1 total and CPS ≥ 1 group using the non-parametric Kaplan-Meier method. Kaplan-Meier plots of TTD will be presented by study intervention. Kaplan-Meier estimates for the median TTD and the first and third quartiles will be presented, along with 95% CIs. CIs for quartiles will be estimated using the Brookmeyer-Crowley method (1982). The TTD for both treatment groups will be compared by the stratified log-rank test.

A stratified Cox proportional hazard model with Efron's method of tie handling will be used to assess the magnitude of the treatment difference (i.e., the hazard ratio). The hazard ratio and its 95% confidence interval from the stratified Cox model with a single treatment covariate will be reported separately for the PD-L1 total and CPS ≥ 1 group. Participants with no post-baseline assessments will be considered censored at day 1 and participants without definitive meaningful clinical deterioration for the PRO score will be treated as censored for that PRO score at the last visit.

Only if GSK3359609 in combination with pembrolizumab + 5FU/platinum-based chemotherapy demonstrates superiority to placebo in combination with pembrolizumab + 5FU/platinum-based chemotherapy in OS in both populations (total and PD-L1 CPS ≥ 1 participants), will key secondary PRO endpoints be tested. The alpha level from OS hypothesis will be propagated to key PRO hypotheses as described in Section 2.2.

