4. STATISTICAL ANALYSES

4.1. General Considerations

4.1.1. General Methodology

The modified Intent-to-Treat (mITT) analysis set will be used for all study population analyses, efficacy analyses and PRO analyses, unless otherwise specified. The safety analysis set will be used for all safety analyses, unless otherwise specified.

Stratified statistical analyses (the stratified logrank test, the stratified Cox model and the stratified max-combo test) will be based on the following stratification factors, PD-L1 expression (CPS ≥ 20 vs. $1 \leq \text{CPS} < 20$ vs. CPS < 1), and HPV status (positive vs. negative). Participants with oropharynx HPV negative/unknown and non-oropharyngeal tumors will be combined as the HPV negative group in the stratified analyses. The analyses will be performed based on the data collected in Interactive Response Technology (IRT) at randomization will be used, even if it is subsequently discovered that these values were incorrect.

In the case of a substantial amount of wrong stratification assigned at the time of randomization, a sensitivity analysis may be performed based on the data collected in the CRF (or vendor data if collected outside of eCRF).

Confidence intervals will use 95% confidence levels unless otherwise specified.

Unless otherwise specified, continuous data will be summarized using descriptive statistics: n, mean, standard deviation (std), median, minimum and maximum. Categorical data will be summarized as the number and percentage of participants in each category.

Unless otherwise specified, subsequent anticancer therapy will include systemic anticancer therapy, follow-up radiotherapy that is not palliative, or on treatment or follow-up cancer-related surgery/procedures that are not palliative or diagnostic in nature.

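### The time-to-deterioration hazard ratios are valid as planned, but a baseline-adjusted hazard ratio should be reported beside them

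*SAP*

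**What the plan says.** Both documents define the event relative to the participant's own starting score. Protocol 9.4.3: "TTD will be defined as the time from the date of randomization to the date of first definitive meaningful deterioration in score compared to baseline". SAP 4.3.1.1 measures time from randomization to the "first definitive meaningful deterioration from baseline in the EORTC IL51 pain domain score", with the matching definition for physical function on PROMIS-PF-8c.

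Both documents fit treatment alone. Protocol 9.4.3 gives the HR from the stratified Cox model with Efron's "method of tie handling and with a single treatment covariate will be reported"; SAP 4.3.1.2 has the HR and its interval "from the stratified Cox model with a single treatment covariate will be reported separately for the PD-L1 total" and CPS≥1 groups. Under SAP 4.1.1, stratified analyses "will be based on the following stratification factors, PD-L1 expression" (three CPS classes) and HPV status.

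The between-arm test is separate from the Cox model: "The TTD for both treatment groups will be compared by the stratified log-rank test". Only if OS is superior in both populations "will key secondary PRO endpoints be tested".

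SAP 4.3.1.1, Table 4, censors at randomization anyone in the row "No or incomplete baseline corresponding PRO assessments". SAP 4.2.3, 4.2.4 and 4.4 drop sensitivity, supplementary and exploratory analyses from the main CSR. The SAP specifies no summary of baseline PRO scores by arm.

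**The concern.** The event is a change from baseline on a bounded scale, so the chance of an event plausibly depends on where a participant starts. Someone with high baseline pain has little room to rise and tends to regress downwards; someone with low baseline pain has more room and tends to regress upwards. For physical function the directions reverse. The arm that starts worse can therefore look better on TTD for reasons unrelated to treatment. PD-L1 and HPV strata do not capture baseline pain or function.

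What is at stake is how the reported effect size is read. SAP section 1 puts all secondary endpoints in the main CSR, and SAP 4.3.1.2 does not make reporting of the HR conditional on passing the OS gate. If the gate is not passed, the HR is what readers will look at, and nothing specified in the SAP would show them a baseline imbalance.

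**Working it through.** **No plan figure to reproduce.** The documents state no sample size, event count, power or effect size for TTD. The standard error used below, SE(log HR) = 2/√events, can be checked on the plan's PFS figure. With 470 events, HR 0.62 and one-sided alpha 0.01%, it gives 92.8% power against the 93.1% stated in Protocol 9.2.1.

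**Inputs.** From the documents: 1:1 allocation, treatment-only Cox model, event defined as change from own baseline. Assumed, because the documents do not give them: number analysed N = 60 to 640; log HR per SD of baseline score b = 0.2 to 0.6 in size; event fraction f = 40%.

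**Size of the shift.** The chance difference in mean baseline between two equal arms has SD d = 2/√N, in units of the score's SD. A one-SD imbalance multiplies the unadjusted HR by exp(b × d), or by its inverse, depending on direction. The 95% CI half-width factor is exp(1.96 × 2/√(0.4N)).

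| N | d | HR factor, b = 0.2 | HR factor, b = 0.6 | CI half-width factor |
|---|---|---|---|---|
| 60 | 0.258 | 1.053 | 1.168 | 2.23 |
| 100 | 0.200 | 1.041 | 1.127 | 1.86 |
| 300 | 0.115 | 1.023 | 1.072 | 1.43 |
| 640 | 0.079 | 1.016 | 1.049 | 1.28 |

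The range is 1.016 to 1.168, or roughly 2% to 17%.

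**Shift relative to uncertainty.** Shift/SE = (b × 2/√N) / (2/√(fN)) = b√f, so N cancels. At f = 40%, √f = 0.632 and the ratio is 0.13 (b = 0.2) to 0.38 (b = 0.6) of one SE. Divided by 1.96, that is about 6% to 19% of the CI half-width on the log scale, at every trial size.

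**Is b plausible?** The endpoint was simulated with 1,200 trials per setting, N = 100 or 200. Assumptions: a 0–100 score in 12 steps, true SD 22, measurement-error SD 10 or 15, PROs every 3 weeks to week 21 then every 6 weeks, a 10-point threshold and the SAP's definitive rule. The hazard of deterioration fell 24% to 35% per SD higher baseline. The slope of log HR on imbalance was −0.24 to −0.39 unadjusted and −0.07 to +0.01 with baseline in the model. A one-SD imbalance (0.14 to 0.20) moved the HR by about 3% to 7%. In a smaller run (250 trials per setting) with thresholds from 10 to 25 points, the hazard fell 21% to 37% per SD, so the dependence does not hinge on the 10-point choice.

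**Validity and precision.** A separate simulation compared Cox models with and without baseline: 1,500 runs per setting, N = 100 and 300, b = 0, 0.4 and 0.6, HR 1 and 0.72, about 30% events, no strata.

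- Unadjusted under the null: mean HR about 1.00, one-sided rejection 2.0% to 3.0% at nominal 2.5%. CI coverage over all settings was 94% to 96%.
- Slope of log HR on imbalance with b = 0.4 or 0.6: 0.36 to 0.57 unadjusted, −0.05 to 0.01 adjusted.
- SD of log HR at b = 0.6, HR 0.72: 0.389 unadjusted and 0.400 adjusted (N = 100); 0.211 and 0.214 (N = 300).
- Mean HR with true HR 0.72 and b = 0.4 or 0.6: 0.72 to 0.73 unadjusted, 0.70 to 0.72 adjusted.

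**Cost in participants.** Anyone without a complete baseline is censored at randomization, before any event, so requiring the covariate removes nobody who contributes to a risk set.

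**The case against.** The strongest reply is that the treatment-only model is prespecified, identical in protocol and SAP, and the same as that used for OS and PFS. Allocation is randomized and double-blind, so chance imbalance is already inside the confidence interval and the test's error rate. This stands, and the simulated coverage and rejection rates agree with it. A reader might infer that the planned HR is biased or invalid; the documents do not support that.

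A reader might also infer that early termination makes the problem worse. Small arms do give larger imbalances, but they widen the interval in the same proportion: the ratio b√f does not contain N, and a lower event fraction would shrink it.

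Nor are the decisions on H5 to H8 at risk. They rest on a stratified log-rank test gated on OS, and a Cox covariate does not enter it.

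A gain in efficiency is tempting to claim, because one-sided rejection rose by up to 5 points with adjustment (30.3% to 35.1% at N = 300, b = 0.6). But the SD of the log HR did not fall. The adjusted HR is a slightly different quantity (hazard ratios are non-collapsible) and lies a little further from 1.

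Replacing the planned HR outright would change the summary measure in SAP Table 2 and depart from Protocol 9.4.3 after termination. That objection succeeds, so the adjusted HR belongs beside the planned one.

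Finally, SAP Table 1 says PRO analysis details moved to a standalone SAP, which is not among the documents. A supportive adjusted model may already be there.

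**Conclusion.** The point holds as a modest improvement to the reported effect estimate. The plan contains no error or contradiction here. The TTD HR omits the score from which deterioration is measured, the strata do not stand in for it, and this SAP plans no adjusted estimate for the main CSR.

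The 2% to 17% range depends on the assumed N, b and event fraction, and the 3% to 7% figure on the simulated pain-like score. The simulated PRO schedule runs on, although Amendment 2 removed PRO collection from the schedule of activities. Neither simulation used the actual strata. PROMIS-PF-8c was not simulated separately, so the size for physical function is less certain than for pain. The firmer conclusions are that an imbalance in a prognostic baseline shifts the unadjusted HR, that adjustment takes this to about zero, and that the shift is small relative to the interval.

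**What to change.** In SAP 4.3.1.2, keep the stratified log-rank test and the treatment-only HR as planned. Beside them, report a stratified Cox HR with 95% CI from a model with treatment plus the continuous baseline score: the EORTC IL51 pain domain for TTD in pain, PROMIS-PF-8c for TTD in physical function. Do this for the total and CPS≥1 populations, and summarise both baseline scores by arm. Label the added HR as conditional on baseline, list the addition in SAP 1.1, and check it against the standalone PRO SAP so that the two agree.

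The cost is one extra model per endpoint in each population and a baseline table. No new data are needed. The main downside is two HRs per endpoint that can differ slightly even without imbalance, because they estimate slightly different quantities; the label should say so.
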